This study will test the hypothesis that time to remission with treatment of PCT with low-dose hydroxychloroquine is comparable to that with repeated phlebotomy. Although this is not a mechanistic study, the study provides an opportunity for observations in some participants that may enhance our understanding of how 4-aminoquinolines act in PCT. Such efforts to better understand the underlying mechanism are important because they are likely to enhance acceptance of this form of therapy. For example, patterns of porphyrins in urine will be compared during both types of therapy to determine if there is preferential excretion of heptacarboxylate porphyrin, as we observed in chloroquine-treated rats (64). Serum iron, iron-binding capacity and percent transferrin saturation will be measured at each visit to determine if these serum iron markers are affected by low-dose hydroxychloroquine. We will also compare on an optional research basis urinary excretion of iron in participants on each type of therapy, since there is some evidence that chloroquine can mobilize iron from the liver in PCT (48, 55, 59). Hepatitis C plays an important role in many participants with PCT, and it is of interest to know whether or not 4-aminoquinolines might affect this viral infection during treatment of PCT. Therefore, we will measure hepatitis C viral load (serum HCV RNA levels) on an optional basis in

participants with both PCT and HCV during treatment with hydroxychloroquine or phlebotomy. A change in HCV RNA titer may indicate that treatment alters the production and/or release of this virus. Examination of pilot results in these groups of participants will determine if further observations in additional participants are warranted.

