Study initiation. This study was started at UTMB in 2006 with grant support from the FDA Office of Orphan Product Development. It was initially conceived as a randomized noninferiority study, with retention of nonrandomized participants to be treated and followed in a substudy, to provide additional safety data. A planned interim analysis of 48 patients enrolled at UTMB was carried out and published in 2012 (45); 4 additional patients were enrolled after the interim analysis, for a total of 52 enrolled at that site. The study then became a Porphyrias Consortium (PC) study with the same design. Additional subjects have been enrolled, mostly at UTMB. However, the interim analysis and discussions with the DMCC and the DSMB have pointed to a need to amend the study, as in this protocol version.

Results of the interim analysis. We analyzed results from 48 consecutive patients with welldocumented PCT who were also well characterized for susceptibility factors and were prospectively treated by phlebotomy (450 mL, every 2 weeks until they had serum ferritin levels of 20 ng/mL) or low-dose hydroxychloroquine (100 mg orally, twice weekly, until at least 1 month after they had normal plasma levels of porphyrin) (45). Unexpectedly (1) fewer than half of the patients could be randomized, such that more patients were assigned to phlebotomy than hydroxychloroguine, (2) many treatment and study visits were missed, especially with phlebotomy, and this delayed remission, and (3) due mostly to missed study visits near the time of remission, time to achieve a normal plasma porphyrin concentration (the primary outcome) was evaluable in only 30 of 48 subjects (17 treated with phlebotomy and 13 with hydroxychloroquine, see Figure 2). Medium times to the primary endpoint were comparable – between 6 and 7 months for both treatments, when either all of the 30 evaluable patients or only the 17 randomized evaluable patients were analyzed. Noninferiority was not established, and numbers were insufficient to assess effects of individual susceptibility factors on treatment response. Compliance was better with hydroxychloroquine than phlebotomy. It was noted that when plasma porphyrin levels became normal, other measurements, such as urine porphyrin levels and porphyrin patterns, were often still abnormal, suggesting that a normal plasma

[figure not shown]

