Figure 2. Enrollment, assignment to treatment with or without randomization of 48 study patients with PCT in the interim analysis, and inclusion of the 30 patients who achieved a normal plasma porphyrin concentration in the analysis comparing time to remission with phlebotomy and low-dose hydroxychloroquine.

porphyrin level may not be a sign of full remission. Therefore, continuing treatment with

hydroxychloroquine until these additional outcome measures become normal may be beneficial. There were no significant side effects with either treatment. Follow up was insufficient to compare recurrence rates with these treatments.

Based on these interim findings we concluded that (1) the study should continue with changes to better assess response and durability with these two standard treatments. (2) Time to achieving treatment endpoints in addition to normal plasma porphyrin levels should be assessed. (3) All available PCT patients who require treatment should be enrolled, if possible, and assigned treatment based on medical indications, preference, or randomization (for patients suitable for either treatment). (4) A noninferiority design is not appropriate, because most subjects are not randomized, and outcomes should be compared using descriptive methods. (5) Power analyses to assess effects of clinical features and susceptibility factors should emphasize those of greatest clinical interest. We consider that age and sex are the clinical features of greatest interest, and alcohol use, hepatitis C and UROD mutations are susceptibility factors of greatest interest. (6) Longer follow up is needed to assess durability of treatment, and whether this relates to susceptibility factors. (7) The single primary outcome was evaluable in ~2/3 of patients in the interim analysis. Inclusion of additional outcomes is likely to provide evaluable outcomes for a greater proportion of patients. (8) This study also will provide serial data and samples on a cohort of PCT participants in whom treatment responses and complete remission are rigorously documented, which will be valuable for future cross sectional and longitudinal research on the pathogenesis and natural history of this disease.

3. Specific aims

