4.R. Data analysis and statistical considerations. This was originally designed as a randomized noninferiority clinical trial, with inclusion of participants who could not be randomized in a substudy, but with the same treatment and follow up for all participants. We had anticipated that 90% of participants could be randomized, and the intent was to include only randomized participants in the noninferiority analysis. A planned interim analysis, which has been published (45) found that more than half the participants could not be randomized due to medical reasons or patient preference; therefore the interim data was analyzed for the randomized participants and for all participants. Although the treatments appeared equivalent in terms of time to remission, statistical significance was not achieved. Therefore, after formation of the Porphyrias Consortium (PC), the study was continued as a PC study with the goal of enrolling enough participants for a statistically significant result. Based on the interim analysis, the PC investigators identified additional value in continuing this study to enroll a larger number of participants. 1.) Like the PC Longitudinal Study (LS), PC7201, this study enrolls participants with well documented PCT who are characterized for all of the known susceptibility factors. which are multiple but different for individual participants. But unlike the LS, this study carefully documents treatment response and remission, and allows assessment of treatment response and durability as related to specific, multiple susceptibility factors, some of which may change over time. 2.) This study will allow examination of the importance of newly-identified or postulated susceptibility factors, not only for contributing to development of PCT but for affecting treatment responses. 3.) This study is developing for the first time reference information on time to remission for phlebotomy, presently for comparison with hydroxychloroguine. But additional treatment arms may be added to the study as new therapeutic approaches are developed in the future.

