The study will continue as a more pragmatic study relevant to clinical practice, with assignment to treatment based on uniform criteria and randomization only of participants eligible for both treatments, to avoid unnecessary bias. Therefore, it will be a two-group study with no substudy. A descriptive approach to data analysis will be employed, with clinically relevant comparisons of the two treatments, rather than a noninferiority analysis.

Inclusion of all available participants rather than just the minority that can be randomized has a number of advantages. Participants eligible for both treatments (and therefore eligible for randomization) might respond differently than those who are not, since some of the reasons that make participants ineligible for one treatment relate to certain susceptibility factors and to prior treatment experience. Exclusion of a majority of participants from treatment comparisons also would make the study less pragmatic and less clinically relevant. In the interim analysis, randomized and nonrandomized participants did not differ in terms of clinical and demographic

features, but such important comparisons would be more meaningful with a larger number of participants. In the amended study, participants who are eligible for both treatments are to be randomized as a method for choosing between treatments that is needed in the study to avoid bias, but not as a study design feature. Bias might arise, for example, from existing site-specific treatment preferences.

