A total of at least 100 participants will be assigned, based on medical criteria, preference, or (if eligible for both treatments) by randomization, to one of these standard treatment groups. CRFs will be completed for each patient, including porphyrin levels, and data entered into the study database. This database is designed by and housed at the Data Management and Coordinating Center (DMCC) at the University of South Florida in Tampa. The DMCC is supported by the NIH Rare Diseases Clinical Research Network and serves as the secure repository for de-identified data for all consortia in the Network. Upon approval from the UTMB IRB and the Porphyrias Consortium DSMB, data from patients previously enrolled in this study at UTMB starting in 2006 before the study was a RDCRN study will be entered into the database. Subjects will be contacted to give their consent for this data transfer to the DMCC and storage in a federal data repository. For subjects who are now deceased consent will be obtained from next of kin. For subjects who cannot be re-contacted or where the next of kin cannot be re-contacted, approval of the UTMB IRB and the Porphyrias Consortium DSMB will be sought for this data transfer. Transferring this previously collected de-identified data is not expected to cause any increased risks to subjects. Data will be verified and edited where necessary for completeness and consistency by comparison with source documents. Study outcomes, such as time to achieving biochemical endpoints, will be determined from this data. As was found in the interim analysis, assignment to the two groups is unlikely to be equal, and more will be assigned to phlebotomy than to hydroxychloroquine. As in the interim analysis, times to achieving measures of remission are not expected to be substantially different for the two treatment groups. Effects of multiple susceptibility factors and other clinical and demographic features on treatment response and durability will be further examined. Outcome measures such as time to remission will be compared using Cox proportional models to study the effects of susceptibility factors on the hazard ratio to compare the two treatments. All patients who start treatment will be included in the analysis. Safety measures will be compared more descriptively where the adverse effects of each type of treatment are different.

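### The protocol says it will test that time to remission is comparable, but section 4.R gives no way to judge comparability, so a non-significant hazard ratio could be read as showing it

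*Combined protocol and SAP*

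**What the plan says.** Comparability of time to remission is the stated hypothesis in several current sections. Section 2 (Background) says "This study will test the hypothesis that time to remission with treatment of PCT with low-dose hydroxychloroquine is comparable to that with repeated phlebotomy". Section 3 (Specific aims) makes it the primary working hypothesis and introduces the aims as the means of testing it. The end of 1.A calls it the continuing working hypothesis, and 1.B gives the purpose as finding out whether hydroxychloroquine brings remission as fast and as safely as phlebotomy.

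The analysis was deliberately changed after the interim look. Section 2 concludes "A noninferiority design is not appropriate, because most subjects are not randomized, and outcomes should be compared using descriptive methods", and 4.R carries this through: "A descriptive approach to data analysis will be employed, with clinically relevant comparisons of the two treatments, rather than a noninferiority analysis". Time to remission is nonetheless to be "compared using Cox proportional models to study the effects of susceptibility factors on the hazard ratio to compare the two treatments", with the expectation that "times to achieving measures of remission are not expected to be substantially different for the two treatment groups".

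On the interim data, section 2 reports "Noninferiority was not established, and numbers were insufficient to assess effects of individual susceptibility factors on treatment response", while 4.R says "Although the treatments appeared equivalent in terms of time to remission, statistical significance was not achieved". The published interim report (reference 45) carries a title that credits low-dose hydroxychloroquine with the same effectiveness as phlebotomy.

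The Sample Size and Power paragraph of 4.R gives 80% power with 90 subjects for HRs of 1.9 to 3.2, each tied to a susceptibility factor, and ends with about 50 subjects per group. It gives no figure for the treatment contrast.

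**The concern.** A hypothesis that two treatments are comparable needs a statement of how different they may be, or at least of how the confidence interval will be read. The plan has neither. It sets no significance level or interval level for the treatment contrast, and it does not say what comparable or substantially different means. The reference to about 50 subjects per group may also suggest that the treatment contrast was sized, when the calculation concerned other effects.

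In that gap, a treatment HR that is not significantly different from 1 is easily taken as support for the hypothesis. The interim wording shows that this is not a remote risk: noninferiority was not established, yet the treatments were described as appearing equivalent. More than wording is at stake, because the protocol expects its results to guide choice of treatment, inform guidelines and support future labeling for hydroxychloroquine.

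**Working it through.** **The plan's own figure.** There is none for the treatment contrast. The factor figures can be checked roughly with the Schoenfeld form, power = Φ(√(d·p(1−p))·|ln HR| − 1.96). This assumes d = 90 events and two-sided 0.05, because neither the event count nor alpha is stated. Prevalences are from Table 2 and the text after it.

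- Alcohol (87%, HR 2.3): √(90×0.87×0.13) = 3.19; 3.19×0.833 − 1.96 = 0.70; power 76%.
- Hepatitis C (69%, HR 2.0): √(90×0.69×0.31) = 4.39; 4.39×0.693 − 1.96 = 1.08; power 86%.
- By the same formula: smoking 84%, HFE 86%, UROD 76% at 13% prevalence or 89% at 20%.

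These lie near 80% but are not reproduced by one set of inputs. They say nothing about hydroxychloroquine against phlebotomy.

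**Precision of the treatment HR.** Inputs:

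- Split 17:13, from the interim evaluable patients (section 2), so p(1−p) = (17/30)(13/30) = 0.2456.
- Events: 90 (the figure in 4.R), 100 (planned enrollment), and 63 as a low scenario (interim evaluability 30/48 = 62.5% of 100).

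Factor by which the estimate is multiplied and divided = exp(1.96/√(d×0.2456)):

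| Events | √(d×0.2456) | Factor | 95% CI if observed HR = 1 |
|---|---|---|---|
| 100 | 4.96 | 1.49 | 0.67 to 1.49 |
| 90 | 4.70 | 1.52 | 0.66 to 1.52 |
| 63 | 3.93 | 1.65 | 0.61 to 1.65 |

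**In months.** Take a phlebotomy median of 6.5 months, the middle of the 6 to 7 months reported at the interim. An HR limit becomes a ratio of medians equal to the factor if times are exponential, or to its square root if Weibull with shape 2. The documents give no shape, so both are assumptions.

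- 90 events, exponential: 6.5/1.52 to 6.5×1.52 = about 4.3 to 9.9 months.
- 90 events, Weibull shape 2: √1.517 = 1.232, so 6.5/1.232 to 6.5×1.232 = about 5.3 to 8.0 months.
- 63 events: about 3.9 to 10.7 months (exponential) or 5.1 to 8.3 (shape 2).

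**How often a real delay would be non-significant.** Suppose the true HR is 2/3, a remission rate 1.5 times slower on hydroxychloroquine. Then P(p>0.05) ≈ Φ(1.96 − √(d×0.2456)×ln 1.5).

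- 90 events: 1.96 − 4.70×0.405 = 0.05; probability 52%.
- 63 events: 1.96 − 3.93×0.405 = 0.37; probability 64%.

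That HR corresponds to a median of 6.5×1.5 = 9.75 months if exponential, or 6.5×√1.5 = 7.96 months under shape 2. The smallest HR detectable with 80% power is exp(2.80/4.70) = 1.81 with 90 events and exp(2.80/3.93) = 2.04 with 63.

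**The case against.** The strongest reply is that the analysis is descriptive by reasoned choice, because most participants are not randomized, and that a margin would not cure confounding. That stands, and nothing here asks for a margin. The synopsis objective and 4.B also speak of determining and comparing time to remission, which estimation can meet. It would go too far to say that the study cannot answer its primary question. The difficulty is confined to the sections that promise a test of comparability.

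Four stronger readings are tempting and should be resisted.

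- **That the plan will conclude comparability from p>0.05.** No passage says so. Section 2 states that noninferiority was not established, and 1.A says the interim analysis did not show the treatments comparable in all important respects. The misreading is a risk, not a stated intention.
- **That the study is now pursuing significance.** The phrase "with the goal of enrolling enough participants for a statistically significant result" is past-tense and describes continuation as a Consortium study, which section 2 says began with the same design. The amended plan follows it, so it should not be held against the current analysis.
- **That a Cox model cannot show comparability.** An HR with its CI is a standard basis for such a claim. What is missing is a rule for reading the interval.
- **That the exponential month range is the precision.** Section 2 puts target ferritin at 3 to 4 months and remission at 6 to 7, so a constant hazard from day one is doubtful for phlebotomy. Under shape 2 the range is roughly half as wide.

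The 63-event case is also pessimistic. The revised protocol adds visit practices to capture the 4-week window and analyzes everyone who starts treatment. The 90-event figures make the point alone.

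**Conclusion.** The concern holds in a limited form. The protocol commits to testing comparability, but it supplies neither a meaning for the term nor a way to judge it, and it states no precision for the treatment contrast. With 90 to 100 events the 95% CI for the HR would be the estimate multiplied and divided by about 1.5. A 1.5-fold slower remission rate would then miss significance about half the time with 90 events. Non-significance would therefore be weak support for comparability.

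These figures assume the interim split, one event per counted participant, the Schoenfeld approximation and no covariate adjustment. They describe random error only. Because most assignment is by medical criteria or preference, real uncertainty is larger. The month ranges depend on assumed distributions, so the HR scale is the safer statement. This should be corrected because it limits what the trial can conclude. It does not call for a return to noninferiority.

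**What to change.** In 4.R:

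- Report the treatment HR and the difference in restricted mean or median time to remission, each with a 95% CI. Adjust for the factors that drive non-random assignment, such as ferritin, HFE genotype, liver tests and alcohol use from Table 3.
- State that comparability will not be concluded from p>0.05, and that any statement about it will quote the largest delay the CI does not exclude.
- Give the expected CI width for about 90 to 100 participants, and say that the existing power figures concern susceptibility factors only.

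In sections 2 and 3, replace the language of testing comparability with language of estimating the difference in time to remission. Marking the pre-amendment goal in 4.R as historical would remove a further ambiguity.

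This needs no new participants, visits or data, and no margin. It adds a modest amount of analysis, namely the adjusted time difference and a precision statement, and it makes the eventual claim more modest.

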centers in the U.S. The laboratory uses published methods and reports results with a clinically useful interpretation (70-72). Other laboratories can be used if equivalent results can be obtained. Although results from different laboratories are likely to be comparable, this has not been verified. Normal ranges are likely to be less comparable between laboratories than elevated abnormal values. It is desirable to use the same laboratory for porphyrin testing throughout the study. In general, Quest, LabCorp, ARUP or Mayo are suitable for urine and plasma porphyrin measurements. However plasma porphyrin fluorescence peak testing is only done at UTMB and ARUP. The treatment outcomes are based on criteria stated in this protocol rather than on normal ranges stated by different laboratories, which may vary considerably.

Molecular analyses to identify *UROD* mutations are provided by the Genetic Testing Laboratory at the Icahn School of Medicine at Mount Sinai in New York City.

4.B. Design. This is an open-label comparative study of the two standard treatments for PCT. Participants will be assigned to the treatment for which they are eligible, as determined by strict medical criteria as outlined in this protocol. Participants eligible and willing to receive either treatment will be randomized across sites; however the majority of participants are expected to be assigned a treatment based on their medical indications and preference. Based on many decades of clinical experience, both treatments are accepted as effective and safe. Therefore, comparing efficacy and safety will not be an objective of these standard of care treatments. Rather, the main objectives will be to compare time needed to achieve remission, as assessed by documented primary and secondary biochemical and clinical outcomes, and the durability (i.e. lack of disease recurrence) after each treatment. Since phlebotomy and low dose hydroxychloroquine are both considered accepted alternatives for treatment of PCT, costs will be either considered standard of care and charged to insurance or supported by the Porphyrias Consortium grant for those participants without insurance.

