Liver ultrasound and biopsy will be recommended to participants based on clinical indications per the investigator, these tests will not be done solely for the study. If completed at an outside institution records will be obtained. Tissue will be examined microscopically, and iron content will be measured if possible. Evaluation of liver histology is not required for this study because the results are usually not essential for diagnosis or classification of PCT participants, identifying risk factors, or deciding on treatment options. However, liver biopsy is the best means of assessing liver iron concentration, and is often recommended for assessing the degree of pretreatment damage to the liver associated with hepatitis C, alcohol, steatosis, etc. Results of liver biopsy, when available, will be recorded on the CRFs and tabulated and analyzed with other clinical information that pertains to PCT.

Treatment assignment. Before assigning treatment, subjects will be evaluated for the contraindications to treatment with hydroxychloroquine and phlebotomy listed in Table 3 and 4.

If one of these treatments is contraindicated, the reason(s) will be recorded, and the subject will be assigned to the other treatment. Participants eligible for both will be assigned by randomization.

Table 3. Contraindications to treatment with hydroxychloroquine.

- 1. Unwillingness to consider this form of treatment
- 2. Lactating women
- 3. Psoriasis
- 4. Significant retinal disease
- 5. Glucose-6-phosphate dehydrogenase deficiency
- Recent and continued heavy use of alcohol (defined as 28 or more drinks per week)
- 7. Recent and continued use of hepatotoxic drugs such as acetaminophen, isoniazid or valproic acid
- Marked abnormalities in liver function tests at baseline, such as serum bilirubin >3mg/dL, serum alanine aminotransferase >200 U/L, or prothrombin time >16 seconds (or INR >1.4)
- 9. Advanced renal disease, with serum creatinine >3 mg/dL
- 10. Poor tolerance or poor response to this treatment in the past
- 11. HFE genotypes C282Y/C282Y or C282Y/H63D and serum ferritin above the normal range (>336 ng/mL)
- 12. Substantial iron overload, with serum ferritin >500 ng/mL, in the absence of these *HFE* genotypes
- 13. Marked iron overload (3+ or 4+) on liver biopsy, if available

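### The pooled Cox comparison has no site term, although the protocol names site preference as a bias and randomises only a minority; stratifying by UTMB versus other sites is a cheap improvement

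*Combined protocol and SAP*

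**What the plan says.** All references are to the combined protocol and SAP.

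- **Bias named.** Section 4.R explains why dual-eligible participants are randomised: "Bias might arise, for example, from existing site-specific treatment preferences". The remedy is "randomization only of participants eligible for both treatments, to avoid unnecessary bias".
- **Who is randomised.** Section 4.B: "Participants eligible and willing to receive either treatment will be randomized across sites". It foresees that most of the cohort will instead receive a treatment chosen on medical grounds or by preference. Section 4.R reports that more than half could not be randomised at the interim analysis, for medical reasons or patient preference.
- **How preference enters.** The first contraindication in Table 3 (hydroxychloroquine) is "Unwillingness to consider this form of treatment". Table 4 has the equivalent for phlebotomy. A participant with a contraindication to one treatment is assigned the other.
- **Analysis.** Section 4.R: "Outcome measures such as time to remission will be compared using Cox proportional models to study the effects of susceptibility factors on the hazard ratio". Everyone who starts treatment is included. Other clinical and demographic features are mentioned, but no site or laboratory covariate, stratum or sensitivity analysis appears in 4.R or the synopsis.
- **Laboratories.** Section 4.A: "Although results from different laboratories are likely to be comparable, this has not been verified". It expects agreement to be weaker for normal ranges than for clearly raised values. It also applies fixed protocol criteria in place of each laboratory's own range, and prefers, without requiring, one laboratory throughout.
- **Site shares.** Background, on study initiation: 52 participants were enrolled at UTMB before the study became a consortium protocol, and then "Additional subjects have been enrolled, mostly at UTMB". Section 4.D projects about 60 further participants, 40-50 of them at UTMB.

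**The concern.** The protection against site preference covers the randomised minority, while the hazard ratio is estimated in everyone. If sites differ both in how often participants receive hydroxychloroquine and in when normalisation is recorded, the pooled hazard ratio mixes a site difference with the treatment difference, and its interval is centred on the wrong value.

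This matters because the working hypothesis is that the two treatments have comparable times to remission. A shift of 5-15% in the hazard ratio could colour that reading in either direction. The descriptive approach in 4.R does not remove the issue, since a treatment hazard ratio is still estimated and the results are meant to inform guidelines and labelling.

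**Working it through.** **1. Is there a route from site to treatment?** Yes, but a limited one. Participants eligible for both treatments are randomised. The rest are assigned by listed medical contraindications or by their own unwillingness. Counselling that differs between sites could affect unwillingness. The documents do not say that it does.

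**2. Is there a route from site to recorded time to remission?** There are three possible ones.
- *Laboratory.* The primary event is falling below a fixed plasma porphyrin limit. A common cut-off removes differences in quoted ranges, but not assay or calibration differences at that cut-off.
- *Visit spacing.* Sections 4 and 4.G let site teams lengthen intervals. The 4-week and 8-week documentation windows and the required laboratory review limit this.
- *Adherence.* Section 4.E leaves travel reimbursement, and cost cover for uninsured participants, to site discretion. Section 4 says adherence significantly influenced time to remission at the interim analysis.

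Visit timing alone is small. Four weeks is 28/30.4 = 0.92 months. On a 6.5-month median (midpoint of the reported 6-7), 6.5/(6.5 - 0.92) = 1.16. At a site hazard ratio near 1.15, the simulated unadjusted treatment hazard ratio stays within about 5% of 1.

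**3. What share is outside UTMB?** From 4.D, 60 - 50 = 10 to 60 - 40 = 20 new participants come from elsewhere. Out of 100, with essentially all earlier participants at UTMB, that is 10-20%. Adding the 60 to the 52 already enrolled gives 10/112 = 9% to 20/112 = 18%, which is much the same.

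**4. How large is the distortion?** The plan has no figure on site to reproduce. Its detectable hazard ratios concern susceptibility factors. A simulation with no true treatment effect used these inputs:
- n = 100, with 80-90% at UTMB (step 3);
- exponential times with median 6.5 months at UTMB;
- censoring at the 24-month treatment limit, plus assumed dropout (exponential, mean 60 months);
- assumed hydroxychloroquine share, UTMB versus elsewhere: 35% versus 60%, or 30% versus 70%;
- assumed remission hazard elsewhere relative to UTMB: 1.3, 1.5 or 2.0.

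| Site hazard ratio | Unadjusted treatment HR | Rejection at 5% | Stratified HR | Rejection, stratified |
|---|---|---|---|---|
| 1.3-1.5 | about 1.03-1.11 | 5-9% | about 1.00 | 4-6% |
| 2.0 | up to about 1.17 | up to about 11% | about 1.00 | 4-6% |

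Hazard ratios are averaged on the log scale. Repeat runs move them by about 0.01 and the rejection rates by about one percentage point.

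A wider set of assumptions shows that the sign is not fixed. With 57% phlebotomy at UTMB (the interim 17:13), 20% or 90% elsewhere, site hazard ratios of 0.5 to 2 and 10-20% outside UTMB, the unadjusted hazard ratio runs from 0.84 to 1.17, with rejection of 5-13%.

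**5. What does stratifying cost?** With share s outside UTMB, overall hydroxychloroquine share p and assignment difference d, R² = s(1 - s)d²/[p(1 - p)], and the standard error grows by about 1/√(1 - R²).
- s = 0.1, 35% versus 60%: p = 0.375, R² = 0.09 × 0.0625/0.234 = 0.024, factor 1.01.
- s = 0.2, 30% versus 70%: p = 0.38, R² = 0.16 × 0.16/0.236 = 0.109, factor 1.06.

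The simulated increase is somewhat larger, about 3-9%, because a stratified model also gives up comparisons between strata. For scale, with 90 events split 17:13 the log hazard ratio detectable at 80% power is 2.80/√(90 × 0.567 × 0.433) = 0.596, a hazard ratio of 1.81. Multiplying 0.596 by 1.03 and by 1.09 gives hazard ratios of about 1.85 and 1.91.

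**The case against.** The strongest reply is that the plan has already aimed its remedy at the right group. Investigator or site preference is not a permitted route to assignment: those outside randomisation need a listed medical reason or their own unwillingness, and the reason is recorded. A reader might infer that site preference acts on most participants. The documents do not support that; they leave open only that sites might influence patient unwillingness.

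A reader might also infer that laboratories differ by site. Section 4.A lists acceptable laboratories without tying any to a site, and samples from any site may go to UTMB. The fixed outcome criteria and the controls on visit spacing narrow the outcome route further.

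On size, putting 30% of participants outside UTMB would raise the rejection rate to as much as 16%, but the enrolment projections point to 10-20%. At that share, and with moderate site effects, the excess rejection is close to simulation noise.

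The plan is also silent on site rather than opposed to adjusting for it, and confounding by indication is probably the larger threat.

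These points reduce the size and priority of the concern. They do not close it: the comparison pools everyone, the plan itself names the bias, and nothing in 4.R handles it outside the randomised minority.

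**Conclusion.** The gap is real and modest. Site-specific preference is named as a bias and countered only for a minority, while the Cox comparison covers all who start treatment without a site term. At the 80-90% UTMB share implied by the documents, the distortion under no true effect is a hazard ratio of about 1.03-1.11 with 5-9% rejection for site hazard ratios of 1.3-1.5. It reaches about 1.17 and 11% only if remission is recorded at twice the rate elsewhere.

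The site effects and the 25- to 40-point assignment differences are assumptions; the documents give neither, so these figures show a range and do not estimate the bias. If either link is absent, there is no bias from site. This is a cheap improvement of low to moderate priority, and it does not show that the planned result would be wrong.

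**What to change.** In 4.R, state that the Cox treatment comparison for the primary and each secondary remission outcome will have its baseline hazard stratified by site (UTMB versus all other sites pooled), with the unstratified result shown beside it. Two strata are preferable to one per site, because only about 10-20 new participants are expected from all the other sites together.

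The cost is a sentence in 4.R and, when assignment differs by site, a standard error about 3-9% larger. No new data are needed. Fixing this before the analysis also removes a later choice over the main estimate.

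It does not adjust for differences among the other sites, for laboratory as distinct from site, or for confounding by indication such as ferritin-based assignment. Those need separate handling.
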